# IRB: 14. Human Subjects Certification from Training.

Provide the names of the members of the research team.

ASU affiliated individuals do not need attach Certificates. Non-xxx investigators and research team members anticipated to manage data and/or interact

with participants, need to provide the most recent CITI training for human participants available at www.citiprogram.org. Certificates are valid for 4 years.

# TIPS for streamlining the review time.

- If any of the study team members have not completed training through XXX CITI training (i.e. they completed training at another university), copies of their completion reports will need to be uploaded when you submit.
- ✓ For any team members who are affiliated with another institution, please see "Collaborating with other institutions"xxx
- The IRB will verify that team members have completed IRB training. Details on how to complete IRB CITI training through xxx

Response:

XXX

# PROCEDURES FOR THE REVIEW OF HUMAN SUBJECTS RESEARCH

#### **General Tips:**

- Have all members of the research team complete IRB training before submitting.
- Ensure that all your instruments, recruitment materials, study instruments, and consent forms are submitted via ERA when you submit your protocol document. Templates are xxx
- Submit a complete protocol. Don't ask questions in the protocol submit with your best option and, if not appropriate, revisions will be requested.
- If your study has undeveloped phases, clearly indicate in the protocol document that the details and materials for those phases will be submitted via a modification when ready.
- Review all materials for consistency. Ensure that the procedures, lengths of participation, dates, etc., are consistent across all the materials you submit for review.
- Only xxx faculty, full time staff may serve as the PI. Students may prepare the submission by listing the faculty member as the PI. The submit button will only be visible to the PI.
- Information on how and what to submit with your study in ERA is xxx. Note that if you are a student, you will need to have your Principal Investigator submit.
- For details on how to submit this document as part of a study for review and approval by the xxx IRB, visit xxx

A cluster randomized controlled trial of an after-school playground curriculum intervention to improve children's physical, social, and emotional health: Study protocol for the PLAYground project

NCT ID not yet assigned

Date: June 20, 2022

Statistical Analysis Plan

Data analysis

Intervention effects on the primary trial outcomes (at each follow-up time point) will be assessed using general linear mixed effects models to account for the clustering of individual measurements within schools. These will include fixed effects for treatment group (intervention vs control), time (baseline and follow-up), and interaction term (intervention x time); include school as a random effect; and be adjusted for covariates related to the outcome (eg, student sex, age). Analyses related to physical, social, and emotional health will be performed with the child (nested within a school) as the unit of analysis. Analysis related to attendance and behavioral change will be performed with the school as the level of analysis. Separate analyses will be performed at each follow-up time point. Schools will be included in analyses if they meet at least 80% adherence to the protocol.

Secondary implementation outcomes will be assessed using descriptive statistics for Healthy Staff and Student survey data (appropriateness and feasibility) and data from monthly observations (fidelity and sustainability). Frequencies, means, and standard deviations will be calculated to describe the distributions, measures of central tendency, and dispersion of item responses. Data from Healthy Staff and Student interviews will be analyzed using a matrix analysis to summarize and organize data in alignment with Proctor's dimensions (adherence, exposure/dose, quality of delivery, component differentiation, and participant involvement), and content analysis to identify salient themes for each school, by school-level income, and collectively among intervention school groups. We will utilize a deductive approach, but allow for additional themes to emerge.

Sample size calculation

The average enrollment of schools in the study district is 610 students. The average enrollment in all 14 after school programs across schools in the study district is 420 students. Using an estimate of a 70% participation rate among after-school programs and assuming 20% loss-to-follow-up, a sample of 7 intervention and 7 control schools will provide a sample of approximately 294 students (147 intervention and 147 control) at follow-up. Assuming an intra class correlation coefficient of 0.05 with 80% power and an alpha of 0.05, the sample will be sufficient to detect an effect size of .370, similar to other school-based PA interventions reporting small overall effects.

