#### Response:

We will recruit all 14 of the after school program schools in xxx Schools to participate in the research. Seven of the schools will receive an intervention in year one and the other seven schools will receive in year two. All schools will participate in assessments during both the fall and spring each year.

We will work with the xxx Schools after school program coordinator to send a recruitment email ( staff\_email\_05.15.22) to the program leaders at the 14 schools. Once the leader agrees to participate, they will send informed consents/assents to parents/guardians of the students in the after school program.

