#### Response:

We are using a crossover pre/post study design where seven after-school programs would receive the intervention in years 1 and 2 and seven schools would serve as matched comparison sites. During year two, the next seven schools would receive the intervention. This tiered approach begins with an initial assessment of the playgrounds to ensure that designs include the research-based elements of balancing, brachiating, climbing, spinning, sliding, and swinging. During years 1 & 2, Healthy School Staff will be trained with the xxx curriculum and the children will be trained as Peer Leaders (Fall Semesters 2022 and 2023) who are enrolled in the after-school program who then become peer leaders for all children during recess at their school.

Assessments include Physical, Social and Emotional Health Assessments administered fall and spring semesters of both years to track student behaviors. Assessments of the after-school setting will be conducted by Xplore program leaders on paper and include observations of all students attending Xplore programs. Assessments during recess would be conducted by recess aides/healthy school staff and would include a random sample of 25 students at recess. No identifying information will be recorded. Assessments will take approximately 5-10 minutes to complete. A copy of the assessment is included (K-6 Assessment).

We will ask the Healthy School Staff to complete a survey each fall and spring semester to learn about their perceptions of the training and playground activities. The survey will take approximately 5-10 minutes to complete. A copy of the staff assessment is included (Healthy School Staff Survey). Healthy School Staff may also be asked to participate in a 30-minute interview each spring semester.

We will ask students to complete a short survey about their physical, social, and emotional health and perceptions of the play activities in the program twice a year. The survey will take approximately 5-10 minutes to complete. A copy of the student assessment is included (Student Survey).

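### Several primary outcomes are each analysed at every follow-up with no hierarchy or multiplicity control; even 3 to 5 outcomes at one wave carry about an 11% to 23% chance of a false positive primary result.

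*SAP*

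**What the plan says.** The Data analysis section of the SAP opens with a mixed model for more than one primary outcome: "Intervention effects on the primary trial outcomes (at each follow-up time point". It then sorts the outcomes by level. For the child: "Analyses related to physical, social, and emotional health will be performed with the child (nested within a school) as the unit of analysis". For the school: "Analysis related to attendance and behavioral change will be performed with the school as the level of analysis". On timing it adds: "Separate analyses will be performed at each follow-up time point". The only outcomes called secondary are those on implementation: "Secondary implementation outcomes will be assessed using descriptive statistics".

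The Sample size calculation section gives one alpha (0.05), one power (80%) and one detectable effect (0.370), described as "similar to other school-based PA interventions reporting small overall effects". The Data analysis section gives no significance level.

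On the number of waves, the response to section 7 of the protocol (Study Procedures) says: "Assessments include Physical, Social and Emotional Health Assessments administered fall and spring semesters of both years to track student behaviors". On the timing of treatment, the response to section 6 (Recruitment Methods) says: "Seven of the schools will receive an intervention in year one and the other seven schools will receive in year two". Section 7 limits accelerometry in the comparison schools to the year in which they serve as controls.

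**The concern.** A team following this text would fit one model per primary outcome per follow-up and obtain a set of treatment-by-time p-values, all with primary status. The plan does not say which of them decides whether the intervention worked, and nothing limits the chance that at least one falls below 0.05 when there is no effect. The sample size supports one test at 0.05. The analysis produces several.

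At stake is how a mixed result would be read. If one domain at one wave reached significance and the rest did not, the SAP would give a reader no way to tell a planned success from the most favourable of several chances.

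**Working it through.** **The plan's own figure.** The documents state no familywise error rate, so there is none to reproduce. The stated effect of 0.370 is for a single test. With 7 schools per arm, 21 children per school and ICC 0.05, the design effect is 1 + 20 × 0.05 = 2.0 and the effective size per arm is 147 / 2.0 = 73.5. The detectable effect is then (1.960 + 0.842) × √(2 / 73.5) = 0.462 with normal quantiles, or 0.503 with t on 12 df. The 0.370 is therefore not recovered from these inputs. That is a separate matter, but it bears on the cost of adjustment.

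**Inputs**
- Outcomes: 3 child-level domains (SAP), or 5 if attendance and behaviour count. One variable per domain is assumed.
- Waves: fall and spring of two years (protocol section 7). Taking fall of year 1 as baseline leaves up to 3 follow-ups.
- Level per test: 0.05, two-sided, borrowed from the sample size paragraph.
- Correlation between test statistics: not in the documents. It is assumed equal for all pairs, at 0, 0.5 or 0.7.
- All null hypotheses true.

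**Formula.** For k independent tests, P(at least one p < 0.05) = 1 − 0.95^k. For example, 1 − 0.95³ = 0.143 and 1 − 0.95¹⁵ = 0.537. For correlated tests, the values are the probability that at least one of k equicorrelated standard normal statistics exceeds 1.96 in absolute value, obtained by simulation and checked by numerical integration.

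| Reading | k | Independent | r = 0.5 | r = 0.7 |
|---|---|---|---|---|
| 3 outcomes, 1 wave | 3 | 14.3% | 12.5% | 10.9% |
| 5 outcomes, 1 wave | 5 | 22.6% | 18.3% | 14.8% |
| 3 outcomes, 3 waves | 9 | 37.0% | 26.9% | 20.2% |
| 5 outcomes, 3 waves | 15 | 53.7% | 36.1% | 25.7% |

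**Sensitivity to the correlation.** With 0.3 between outcomes and 0.5 between waves, the 15 tests give about 46%. At 0.9 throughout, 3 tests give about 8% and 15 tests about 14%.

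**Cost of Holm.** The strictest step uses 0.05 / k. The detectable effect grows by the ratio of quantile sums:
- Normal, k = 3: (2.394 + 0.842) / (1.960 + 0.842) = 1.155
- Normal, k = 5: (2.576 + 0.842) / (1.960 + 0.842) = 1.220
- t on 12 df, k = 3: (2.779 + 0.873) / (2.179 + 0.873) = 1.197
- t on 12 df, k = 5: (3.055 + 0.873) / (2.179 + 0.873) = 1.287

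From the recomputed base, 0.462 becomes 0.534 or 0.564 (normal), and 0.503 becomes about 0.602 or 0.648 (t).

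**The case against.** The strongest reply is that the larger figures rest on counts the plan never gives. Four parts of it stand.

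- The SAP does not list its primary outcomes. Its title names only physical, social and emotional health; attendance and behaviour are primary only because nothing but implementation is called secondary.
- Three controlled follow-ups are doubtful. The comparison schools receive the intervention in year 2, and their accelerometry covers only the control year. If fall of year 1 is baseline, physical activity by accelerometer has one controlled follow-up. For the whole plan, 3 to 5 controlled tests is as fair a reading as 9 to 15.
- The same children and schools are measured repeatedly, so independence is unlikely and 54% is an extreme for 15 tests.
- The SAP sets no threshold for the analyses and nowhere says that any one significant test makes the trial positive. A reader might infer such a rule, but the text does not contain it.

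It can also be argued that distinct outcome domains need no joint error control. That position is debated, but it requires the plan to state separate claims for each domain, and this one does not.

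The reply does not remove the problem. The narrowest reading, three domains at one wave, still gives about 11% to 14% at correlations up to 0.7, more than twice 5%. Nor is the count of five a ceiling: section 7 of the protocol lists observations, a student survey and accelerometry, so a domain may hold more than one variable.

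**Conclusion.** The concern holds in a limited form. The SAP has several primary outcomes, analyses each separately at every follow-up, and has no hierarchy or multiplicity control. This is more than missing detail, because following the text as written yields several unadjusted primary tests.

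The size is conditional on 0.05 per test, one variable per domain and no true effects. At one wave, 3 to 5 outcomes give about 14% to 23% if independent and about 11% to 18% at correlations of 0.5 to 0.7. If all three follow-ups are tested, the figures are 37% to 54% if independent and about 20% to 36% at those correlations.

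A reader might take a rate as high as 54% as the plan's actual error rate. The documents do not support that: it needs five primary outcomes, three controlled follow-ups and independence, none of which they establish. A reader might also infer from the benchmark to physical activity interventions that accelerometer-measured activity should be the sole primary outcome. One phrase in the sample size paragraph does not settle that in a project whose title and stated purpose put social and emotional learning at the centre. The choice belongs to the sponsor.

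**What to change.** List the primary outcomes in the SAP, one variable per domain, and say whether attendance and behaviour are among them. Designate spring of year 1, the follow-up before the comparison schools receive the intervention, as the primary time point. Apply Holm across the primary domains at that wave with a familywise two-sided level of 0.05. Alternatively, the sponsor names one primary outcome of its choice at that wave and treats the rest as secondary. Under either option, report the other waves as estimates with confidence intervals.

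Fewer results can then be called primary. Under Holm with 3 to 5 outcomes, the detectable effect at the strictest step is about 15% to 22% larger with normal quantiles, or 20% to 29% larger with t on 12 df. This matters here because the recomputed single-test effect (0.462 to 0.503) already exceeds the stated 0.370, so the sample size text would need revision as well. Naming a single primary outcome avoids this power cost and, on this point, changes only SAP wording.

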#### Response:

We expect to recruit 294 children in grade three to six from 14 schools in xxx School District (about 21 students per school). We expect to recruit about 150 adults (~10 adults per school).

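### With 7 + 7 schools, the SAP fixes no small-sample test and lists no school-level error for the intervention-by-time term, so the stated alpha of 0.05 is not secured

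*SAP*

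**What the plan says.** The Data analysis section of the SAP specifies "general linear mixed effects models to account for the clustering of individual measurements within schools". The fixed effects are treatment group, time (baseline and one follow-up) and their interaction, adjusted for covariates such as sex and age. School is the only random effect named. Each follow-up is analysed separately, and schools below 80% protocol adherence are left out.

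The sample size section of the SAP rests on "a sample of 7 intervention and 7 control schools", on "80% power and an alpha of 0.05", and on the clustering input "Assuming an intra class correlation coefficient of 0.05". It expects "approximately 294 students (147 intervention and 147 control) at follow-up". Protocol section 5 agrees on cluster size: "about 21 students per school".

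Neither document chooses between REML and ML, names a z or t reference, gives a degrees-of-freedom method, or provides for a permutation test. Neither mentions a random effect for child or for school-by-time. Protocol section 7 calls the control schools matched comparison sites but does not describe how schools were allocated.

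**The concern.** Schools are allocated, so the arm effect has to be judged against variation between schools. With 14 schools and two arms that variation is estimated on 12 degrees of freedom. A z test uses the estimate as if it were known, which makes p-values too small and intervals too narrow for such a contrast.

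A second gap lies in the model. When school enters only as an intercept that is constant over time, it cancels from the change between baseline and follow-up. The intervention-by-time test then has no school-level error at all. Automatic degrees-of-freedom methods do not help, because in that fitted model the contrast depends on residual variance alone.

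At stake is whether the 0.05 in the sample size section is the error rate that the primary analyses would deliver.

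**Working it through.** **Inputs.** From the SAP: 7 + 7 schools, 294 children (147 per arm), ICC 0.05, alpha 0.05, power 80%. Cluster size is 294/14 = 21, as in Protocol section 5. Two-sided testing is assumed, because the SAP does not say. Total SD is set to 1.

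**The plan's own figure.** Design effect = 1 + (21 − 1) × 0.05 = 2.0. Standard error of the arm difference = sqrt(2 × 2.0/147) = 0.165. Detectable effect with z = (1.960 + 0.842) × 0.165 = 0.462. The stated 0.370 therefore does not follow from these inputs. That is a separate matter, and 0.370 is used below only as a reference effect.

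**Step 1: a contrast judged against between-school variation.** If the school variance is never estimated as zero, REML with z rejects a true null with probability P(|t12| > 1.960) = 7.4%. Allowing for truncation at zero, simulation of a balanced random-intercept model at one time point (200,000 trials per setting, 21 children per school) gives:

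| Schools | ICC | REML, z | ML, z | REML, t on J − 2 df | ML, t on J − 2 df |
|---|---|---|---|---|---|
| 14 | 0 | 4.1% | 4.5% | 2.3% | 2.7% |
| 14 | 0.01 | 5.2% | 6.1% | 3.2% | 3.8% |
| 14 | 0.02 | 5.9% | 7.1% | 3.7% | 4.6% |
| 14 | 0.05 | 7.0% | 8.8% | 4.7% | 6.0% |
| 14 | 0.10 | 7.3% | 9.4% | 5.0% | 6.6% |
| 10 | 0.05 | 7.7% | 10.1% | 4.2% | 5.7% |

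J is the number of schools, so the t reference has 12 df for 14 schools and 8 df for 10. The 10-school row shows what could follow if the adherence rule removed four schools, two per arm. ML with t on 12 df still gives 6.0% at the plan's ICC, so REML has to be specified as well as the degrees of freedom.

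The SAP's 294 is also the count before loss: "The average enrollment in all 14 after school programs across schools in the study district is 420 students", and 420 × 0.70 = 294. Taking off 20% leaves 235, or 16.8 per school. At 17 per school and ICC 0.05 the z results are 6.7% (REML) and 8.4% (ML), so the conclusion is the same.

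**Step 2: the interaction as listed.** Each analysis has 2 × 294 = 588 records. Residual df, before covariates, are 588 − 14 − 2 = 572, so z and t practically coincide. The model's variance for the interaction is 4s²/147, where s² is the residual variance. The true variance depends on two quantities that the documents do not give, so the following cases are assumptions:

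- Within-child correlation 0.7, no school-by-time variance. The true variance is (1 − 0.7) = 0.3 times the model variance. Error = P(|Z| > 1.960/sqrt(0.3)) = P(|Z| > 3.58), about 0.03%.
- Neither present. The model is right and the error is 5.0%.
- No child correlation, all school variance (0.05) changing over time. True variance = 4 × (0.05 + 0.95/21)/7 = 0.0544. Model variance is about 4 × 1.0/147 = 0.0272. The ratio is 2.0, and error = P(|Z| > 1.960/1.414), about 17%.

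**Step 3: both gaps together.** If the interaction is given a school-level error, for example by analysing school-level change, but z is kept, the error is again P(|t12| > 1.960) = 7.4%. Correcting the random effects does not remove the need for small-sample degrees of freedom.

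**Step 4: price of the correction.** 2.179/1.960 = 1.112, so unpaired intervals are about 11% wider. At an effect of 0.370, power with z is Φ(0.370/0.165 − 1.960) = Φ(0.283) = 61%. With the noncentral t on 12 df it is 54%, and the detectable effect is 0.504.

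**The case against.** A reader might infer that the trial's nominal 5% tests will reject a true null 7% to 9% of the time. The documents do not support that. The SAP names no z, Wald or likelihood-ratio test, and REML with t on 12 df, which its wording equally allows, gives 4.7%. The 7% to 9% range also depends on the ICC and falls to about 4% to 5% at ICC 0. It belongs to a one-time-point comparison, not to the interaction that the SAP lists.

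Nor can it be said that p-values are too small for every child-level primary outcome. With strong within-child correlation and stable schools, the listed interaction test is very conservative and its intervals are too wide.

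It would also be wrong to say that z tests with a school random effect treat the children as independent replicates. School variance is still in the standard error; only the reference distribution is off. Ignoring clustering altogether at a design effect of 2.0 would give about 17%, not 7%.

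All of this stands, and so does the remark that 12 df assumes an unpaired analysis of all 14 schools. What it does not answer is that the plan permits analyses with materially different error rates, and that the model it does list has no school-level error for its key term.

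**Conclusion.** The concern holds in conditional form. With 14 schools the SAP leaves the estimation method and reference distribution open. If z is used for a between-school contrast, the type I error at ICC 0.05 and 21 children per school is about 7% (REML) to 9% (ML), and about 5% to 6% at ICC 0.01. For the interaction as listed, the error is uncontrolled in either direction: about 0.03% to 17% over the assumed cases. Its actual value cannot be found from the documents, because they give neither the within-child correlation nor the school-by-time variance.

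These figures assume two-sided tests, balanced clusters and normal outcomes. The gap is more than missing detail, since following the listed model does not secure the stated 0.05. It should be corrected in the SAP.

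**What to change.** State in the Data analysis section of the SAP:

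1. Models are fitted by REML.
2. The arm effect is tested in a model where school-level variation is the error for that contrast. Two options are to add child and school-by-time random effects to the listed model, or to analyse follow-up adjusted for baseline with a school random effect.
3. Degrees of freedom are Kenward-Roger or Satterthwaite, never z or residual. Expect about 12 if unpaired and about 6 if analysed as seven matched pairs. With fewer schools the number falls.
4. Each primary result is confirmed by a permutation test on school-level summaries that follows the allocation actually used: C(14,7) = 3,432 allocations if unrestricted, or 2^7 = 128 if within seven pairs. The SAP should therefore describe the allocation.

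No new data are needed. The cost is a revised model statement and a software setting. Unpaired intervals become about 11% wider than with z, and power at 0.370 on the plan's inputs is about 54% instead of 61%.

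### The primary group-by-time model is in effect a change-score analysis; under random allocation, adjusting for baseline would be up to about 20% more efficient, with little or no gain if baseline and follow-up school means correlate strongly

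*SAP*

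**What the plan says.** The SAP's Data analysis section specifies general linear mixed models for the primary outcomes with "fixed effects for treatment group (intervention vs control), time (baseline and follow-up), and interaction term (intervention x time". The models also "include school as a random effect" and are to "be adjusted for covariates related to the outcome (eg, student sex, age". Baseline therefore enters as an outcome row. The baseline value is not named as a covariate, and the two arms are not given a common baseline mean.

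The SAP adds: "Separate analyses will be performed at each follow-up time point". Each fit thus has two time points, baseline and one follow-up.

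A baseline will be available, because Protocol section 6 states: "All schools will participate in assessments during both the fall and spring each year". The SAP's Sample size calculation rests on "a sample of 7 intervention and 7 control schools", 147 children per arm and an intraclass correlation of 0.05. It gives no correlation between baseline and follow-up, for children or for schools.

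On allocation, the SAP title reads "A cluster randomized controlled trial of an after-school playground curriculum intervention", while Protocol section 7 says that "seven schools would serve as matched comparison sites". The protocol describes no randomisation.

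**The concern.** A free group effect plus a group-by-time term estimates the difference between arms in mean change. This fixes the baseline coefficient at 1, whatever the data say about how well baseline predicts follow-up. When allocation is random, chance baseline differences are better removed with an estimated coefficient, or by constraining the arms to one baseline mean. If baseline predicts follow-up only weakly, full subtraction adds noise, and the analysis can be less precise than one that ignores baseline.

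Precision is scarce with seven schools per arm. The baseline data are already being collected, so any loss comes only from the choice of model.

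**Working it through.** **Inputs from the documents.** 7 + 7 schools, 147 children per arm, hence m = 147/7 = 21 per school; ICC 0.05; target effect 0.370 SD; 80% power; alpha 0.05 (two-sided assumed).

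**Assumed inputs.** Correlation over time of 0.6 to 0.9 at school level (CAC) and 0.3 to 0.7 at child level (SAC). Neither is in the documents.

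**The plan's own figure.** The design effect is 1 + 20 × 0.05 = 2.0, so 147/2 = 73.5 effective children per arm. The detectable effect for a follow-up-only comparison is (1.96 + 0.84) × √(2/73.5) = 0.462, not 0.370. Power at 0.370 is about 61% (normal) or 54% (t, 12 df). The stated 0.370 is used below only as the target effect.

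**Step 1: what the model estimates.** A generalised least squares fit to generated complete-pair data, with a school random intercept, unequal school sizes and a sex covariate, gave an interaction of 0.09084. The simple difference in mean change was also 0.09084. A covariate that does not change over time leaves the contrast unaltered.

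**Step 2: large-sample variances**, relative to follow-up only = 1:
- change score (planned): 2(1-r)
- baseline-adjusted: 1-r²
- ratio, adjusted to change: (1-r²)/[2(1-r)] = (1+r)/2, a saving of (1-r)/2

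The change score exceeds 1, and so does worse than ignoring baseline, when r < 0.5.

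**Step 3: r for school means.** r = [m·ICC·CAC + (1-ICC)·SAC]/[1+(m-1)·ICC] = (1.05·CAC + 0.95·SAC)/2.0. For 0.6/0.3 this is (0.63 + 0.285)/2 = 0.46; for 0.9/0.7 it is (0.945 + 0.665)/2 = 0.81.

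**Step 4: small-sample cost.** With 14 school means, the baseline slope is estimated within arms on 12 df. For normal data this multiplies the adjusted variance by 1 + 1/(12-2) = 1.10, so the ratio becomes 1.10(1+r)/2. It reaches 1 at r = 2/1.10 - 1 = 0.82.

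**Step 5: results.** Power is from simulated trials on 14 school means with a true effect of 0.37 SD, using t on 12 df (change) or 11 df (adjusted).

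| CAC/SAC | r | (1+r)/2 | × 1.10 | Power, change | Power, adjusted |
|---|---|---|---|---|---|
| 0.6/0.3 | 0.46 | 0.73 | 0.80 | 51% | 60% |
| 0.8/0.5 | 0.66 | 0.83 | 0.91 | 70% | 74% |
| 0.8/0.7 | 0.75 | 0.88 | 0.96 | 83% | 84% |
| 0.9/0.7 | 0.81 | 0.90 | 0.99 | 91% | 91% |

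Simulated variance ratios agreed with the 1.10 column (about 0.80 to 0.99). In the first row, follow-up only had 54% power, above the planned analysis. In the last row the difference was under one point and slightly favoured the change score. Type I error of the adjusted analysis was 5.0-5.2%.

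**The case against.** The strongest case for the plan has four parts.

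- **The model is standard and unbiased under randomisation.** This stands. A reader might infer that the planned estimate is wrong or biased; nothing in the documents supports that.
- **The gain is easily overstated.** This also stands. The large-sample formula suggests a saving of 10-27% for r from 0.81 to 0.46, and a reader might conclude that adjustment is never less precise. With 14 schools neither holds: the saving is roughly 0-20%, and above r of about 0.82 adjustment on school means has the larger variance. The material gain in power sits at the low end of the assumed correlations.
- **Allocation is unsettled.** If schools were matched but not randomised, change and baseline-adjusted analyses can estimate different things, and difference-in-differences is a defensible primary analysis. This limits the point. It does not defeat it, because the SAP presents the trial as cluster randomised and the fix keeps the interaction estimate.
- **The random effects need attention first.** With school as the only random effect, the model-based variance of the interaction is about 4 × 0.95/147 = 0.0259 whatever the correlation over time. The actual variance, (2/7)[2 × 0.05 × (1-CAC) + 2 × 0.95 × (1-SAC)/21], is 0.0295 for 0.6/0.3 and 0.0109 for 0.8/0.8. The reported standard error can therefore be too small or too large, and the power figures above, which use valid school-level tests, do not describe the inference that the SAP's model would give. That is a separate defect. Repairing it leaves a change-score contrast. The exact equality in Step 1 also assumes complete pairs, whereas the SAP allows for 20% loss.

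A reader might also suppose that 0.370 already presumes baseline adjustment, since 0.462 × √(1-0.6²) = 0.370. The SAP states no such input, so the match cannot be relied on.

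**Conclusion.** The point holds as a conditional efficiency gain. The planned model subtracts baseline in full. If allocation is random, baseline adjustment would cut the variance of the effect by roughly 0-20% at this number of schools, for assumed r of 0.46 to 0.81. Power at 0.37 SD would rise by up to about 9 points when r is low and be essentially unchanged at r of about 0.75 or more. Below r = 0.5, the planned contrast is less precise than ignoring baseline.

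The size rests on correlations that the documents do not give, on 21 children per school, on the SAP's ICC of 0.05, and on random allocation. The change is worth making because it costs little and protects against the low-r case.

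**What to change.** Amend the SAP's Data analysis section before outcome data are analysed:

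1. For outcomes linked by study ID, make the primary analysis the follow-up value regressed on arm, the child's own baseline and the school-mean baseline, with school as a random effect. Alternatively, use a longitudinal model with one baseline mean common to both arms, which keeps children who lack one wave. State which outcomes are linked: Protocol sections 7 and 11 make this clear for accelerometry, but it should be confirmed for the student survey.
2. For outcomes analysed by school (attendance, behaviour referrals), adjust for the school's baseline value.
3. Keep the intervention-by-time estimate as a pre-specified sensitivity analysis.
4. State how schools were allocated, reconciling the SAP title with Protocol section 7. If allocation was not random, reconsider which analysis is primary.

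The change is to wording and needs no new data. It spends one degree of freedom on the school-level baseline slope and gains little or nothing if r is high. If allocation was not random, it changes the quantity being estimated, and the retained sensitivity analysis would help to show this.
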